16.3 Methods for Randomization and Stratification

This is a pilot study, so there will be no randomization.

16.4 Outcome Measures

The main outcome measure is 2 yr locoregional control in cetuximab responders.

Secondary outcomes include percent of patients who progress during 3 weeks of neoadjuvant cetuximab by CT RECIST 1.1 criteria, and 2 yr locoregional control for non-responders to neoadjuvant cetuximab.

Other outcomes are molecular correlates. The study is powered only for the main outcome measure. Secondary outcome measurements are descriptive.

16.5 Statistical Analysis

Most of our endpoints for this study are descriptive, and the study is only powered for the primary endpoint. We will report

1. Locoregional control at 2 years for cetuximab responders
2. Percentage of patients who progress during neoadjuvant cetuximab per RECIST 1.1 CT criteria
3. Locoregional control at 2 years for non-responders to cetuximab. We will perform preplanned subset analysis on locoregional control at 2 years for patients who are HPV + vs -.

16.6 Assumptions

The main assumption is that the population in the Bonner trial (EBRT +- cetuximab) and the population involved in this protocol are similar in susceptibility to cetuximab, so that the percentage of patients who develop cetuximab related folliculitis in response to cetuximab will be somewhat similar (it was about 60% in the Bonner trial).

The other assumption is that the percentage of HPV+ and – patients in the Bonner trial is comparable to that in this protocol. This is very difficult to judge, since in the Bonner trial they did not check HPV status. Furthermore, HPV status seems to depend to some degree on race, as African Americans appear to be more often HPV- than whites.

16.7 Compliance and Missing Data

Compliance is defined as adhering to the protocol treatment plan, follow up imaging and appointments for at least 2 years following radiation therapy.

16.8 Interim Analysis

The expected number of patients accrued over the study duration is 27. We expect the response rate is about 60%.

The early stopping rule is determined by the posterior probability of the progression rate greater than 20%. We also assume the non-informative prior on the progression rate. The stopping

would be triggered when the posterior probability of the progression rate no less than 20% is greater than 90%. The posterior distribution of the true progression rate given that k responders are observed out of the first n patients is a beta distribution with shape parameter $1+k$ and scale parameter $1+n-k$. *The first monitoring will be done after 12 patients* and then after every subsequent patient. For example, if 4 or more patients out of the first 12 showed progression, then the trial will be stopped (The table highlights the posterior probability being greater than 90%).

n = number of patients

k = number of the responders.

Each cell contains a posterior probability that the true progression rate is greater than 20% given that k responders are observed out of the first n patients.

| n\k | 0 | 1 | 2 | 3 | 4 | 5 | 6 | 7 | 8 |
|-----|-------|-------|-------|-------|-------|-------|-------|-------|-------|
| 5 | 0.262 | 0.655 | 0.901 | 0.983 | 0.998 | 1.000 | | | |
| 10 | 0.086 | 0.322 | 0.617 | 0.839 | 0.95 | 0.988 | 0.998 | 1.000 | 1.000 |
| 11 | 0.069 | 0.275 | 0.558 | 0.795 | 0.927 | 0.981 | 0.996 | 0.999 | 1.000 |
| 12 | 0.055 | 0.234 | 0.502 | 0.747 | 0.901 | 0.970 | 0.993 | 0.999 | 1.000 |
| 13 | 0.044 | 0.198 | 0.448 | 0.698 | 0.87 | 0.956 | 0.988 | 0.998 | 1.000 |
| 14 | 0.035 | 0.167 | 0.398 | 0.648 | 0.836 | 0.939 | 0.982 | 0.996 | 0.999 |
| 15 | 0.028 | 0.141 | 0.352 | 0.598 | 0.798 | 0.918 | 0.973 | 0.993 | 0.999 |
| 16 | 0.023 | 0.118 | 0.31 | 0.549 | 0.758 | 0.894 | 0.962 | 0.989 | 0.997 |
| 17 | 0.018 | 0.099 | 0.271 | 0.501 | 0.716 | 0.867 | 0.949 | 0.984 | 0.996 |
| 18 | 0.014 | 0.083 | 0.237 | 0.455 | 0.673 | 0.837 | 0.932 | 0.977 | 0.993 |
| 19 | 0.012 | 0.069 | 0.206 | 0.411 | 0.63 | 0.804 | 0.913 | 0.968 | 0.99 |
| 20 | 0.009 | 0.058 | 0.179 | 0.37 | 0.586 | 0.769 | 0.891 | 0.957 | 0.986 |
| 21 | 0.007 | 0.048 | 0.154 | 0.332 | 0.543 | 0.733 | 0.867 | 0.944 | 0.98 |
| 22 | 0.006 | 0.04 | 0.133 | 0.297 | 0.501 | 0.695 | 0.84 | 0.928 | 0.973 |
| 23 | 0.005 | 0.033 | 0.115 | 0.264 | 0.46 | 0.656 | 0.811 | 0.911 | 0.964 |
| 24 | 0.004 | 0.027 | 0.098 | 0.234 | 0.421 | 0.617 | 0.78 | 0.891 | 0.953 |
| 25 | 0.003 | 0.023 | 0.084 | 0.207 | 0.383 | 0.577 | 0.747 | 0.869 | 0.941 |

Note that the prior distribution will be updated based on the number of events observed at each monitoring, and resulting posterior probability of the progression rate greater than 20% will also be updated. The PI will contact with Biometrics division to obtain the updated table after each scheduled monitoring.

17. Human Subjects

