1.2 Secondary Endpoint(s)

1.2.1 Assess secondary clinical endpoints such as the percent of patients receiving neoadjuvant cetuximab who progress by CT RECIST 1.1 criteria during the neoadjuvant cetuximab. All patients in the protocol will receive a CT with IV contrast prior and also after neoadjuvant cetuximab. Progression will be gauged using the RECIST 1.1 CT criteria for progression (at least a 20% increase in the sum of the LD of target lesions, taking as reference the pre-cetuximab scan or the appearance of one or more new lesions). If it is found that the prior probability that 20% or more of the patients are progressing during neoadjuvant cetuximab is at least 90%, the protocol will be stopped (section 16.8). The first interim analysis will be performed after 12 patients. We will also assess the 2 yr locoregional control for non-responders to neoadjuvant cetuximab. We will also assess the complete response rate to PET/CT scan 3 months after the completion of radiation therapy for both responders and for

non-responders to neoadjuvant cetuximab, as PET/CT has a NPV of 95% in this setting, so will give a very good indication of eventual locoregional control.³

1.2.2 Molecular correlates. All patients must have a biopsy of the locoregional disease (primary site or neck lymph nodes), and of the skin prior to therapy. When feasible, patients will also have another biopsy of the locoregional disease and skin after 3 weeks of neoadjuvant cetuximab but prior to starting radiation therapy. If there is a locoregional recurrence, a third biopsy of locoregional disease is possible. The second biopsy after neoadjuvant cetuximab and third biopsy in case of recurrence are strongly recommended but not absolutely necessary for participation in the protocol. Therefore, this protocol offers a unique chance to investigate molecular correlates because 1) the neoadjuvant therapy is a single agent, as opposed to a chemotherapy cocktail (and so the change in protein production is due to a single agent as well), 2) we will obtain normal tissue (skin) samples and tumor samples from before and after 3 weeks of cetuximab, so we will have in-vivo tissue to analyze after this single agent.

Our goals in the molecular analysis are to explore the following possibilities:

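### No progression check is made before patient 12, so patients can still enter the neoadjuvant window after a 4th progression has made the plan's own stop certain

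*Combined protocol and SAP*

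**What the plan says.** Section 16.8 bases early stopping on the progression rate during neoadjuvant cetuximab. It takes a flat prior ("We also assume the non-informative prior on the progression rate") and a Beta(1+k, 1+n−k) posterior. Stopping "would be triggered when the posterior probability of the progression rate no less than 20% is greater than 90" per cent.

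The timetable is "The first monitoring will be done after 12 patients" "and then after every subsequent patient". Section 1.2.1 agrees: "The first interim analysis will be performed after 12 patients". The first boundary is spelled out in 16.8: "if 4 or more patients out of the first 12 showed progression, then the trial will be stopped".

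The table in 16.8 also prints rows for n = 5, 10 and 11, but no look is attached to them. Section 14 provides for general monitoring and audit under the institutional plan and contains no progression check. No section says what happens if a 4th progression is seen before patient 12.

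**The concern.** The patient-12 rule depends only on whether the number of progressions has reached 4, and that number can only rise. If the 4th progression occurs at patient 5, 8 or 11, the outcome of the patient-12 look is already known. Patients entered between that point and patient 12 cannot change it.

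Section 7.1 identifies the neoadjuvant cetuximab as the experimental part of the treatment. Section 17.2 names delay of definitive treatment in patients who do not respond to it as the possible added danger. The patients are previously untreated and non-metastatic (5.1.2, 5.2.1, 5.2.3). The progression rule is the plan's trial-level limit on this risk. As written, it allows new patients to enter the window after its own decision is fixed.

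**Working it through.** **Inputs.** First look at n = 12, and at every patient after that (16.8, 1.2.1). Stop when P(rate > 0.20) exceeds 0.90 under Beta(1+k, 1+n−k) (16.8). Planned total 27 (16.8), accrued uniformly over three years (16.2), so 27/36 = 0.75 patients per month. Progression is read on a CT at day 14-21 after the first dose (7.2.3.2). The true progression rate p is not given; 10% to 50% is an assumed range, and 20% is the rule's own reference rate.

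**1. Reproduce the plan's boundary.** At n = 12 the posterior probability is 0.747 for k = 3, 0.9009 for k = 4 and 0.970 for k = 5. The plan prints 0.901 for k = 4, so the boundary is exactly 4. All printed cells reproduce (largest difference 0.0005).

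**2. Is the criterion met earlier?** With k = 4 the posterior probability for n = 4 to 11 is 0.9997, 0.998, 0.995, 0.990, 0.980, 0.967, 0.950 and 0.927. It is above 0.90 at every n, so a 4th progression before patient 12 satisfies the plan's own criterion when it occurs as well as at patient 12.

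**3. How often, and how many patients?** Let T be the number of the patient in whom the 4th progression occurs:

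P(T = t) = C(t−1, 3) p⁴ (1−p)^(t−4).

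The stop is fixed early if T ≤ 11, and 12 − T patients are then still to enter before the look. For example, at p = 0.5, P(T = t) for t = 4 to 11 is 0.0625, 0.1250, 0.1563, 0.1563, 0.1367, 0.1094, 0.0820 and 0.0586, which sum to 0.887. Weighting by 12 − t gives 0.500 + 0.875 + 0.938 + 0.781 + 0.547 + 0.328 + 0.164 + 0.059 = 4.19 patients.

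**4. Effect of acting at the 4th progression.** An exact recursion to N = 27, with and without this change, gives:

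| Assumed true rate | Stop fixed before patient 12 | Stop at patient 12 (plan) | Mean spared per trial | Mean spared, trials stopping at 12 | Overall stop probability, either way | Expected number entered, plan → changed |
|---|---|---|---|---|---|---|
| 10% | 0.019 | 0.026 | 0.05 | 1.9 | 0.032 | 26.56 → 26.51 |
| 20% | 0.161 | 0.205 | 0.48 | 2.4 | 0.301 | 23.22 → 22.74 |
| 30% | 0.430 | 0.508 | 1.48 | 2.9 | 0.717 | 17.87 → 16.39 |
| 40% | 0.704 | 0.775 | 2.83 | 3.6 | 0.943 | 14.04 → 11.21 |
| 50% | 0.887 | 0.927 | 4.19 | 4.5 | 0.995 | 12.47 → 8.28 |

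The mean spared per trial equals the fall in expected number entered (for example 17.87 − 16.39 = 1.48). The most that can be spared is 8 (T = 4), which is 8/0.75 = 10.7 months of planned accrual.

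**5. Lag.** The table assumes that each CT result is known before the next patient enters. In 21 days about 0.75 × 21/30.4 = 0.5 patient enters, so the real saving is somewhat smaller.

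**The case against.** **Choice of first look.** The strongest objection is that a minimum sample before the first formal look is a legitimate design choice. That holds against adding looks. A reader might infer from the early table rows, where 2 of 5 already gives 0.901, that the plan ought to stop from patient 5. The documents do not support this. No look is attached to those rows, and applying the 0.90 rule from n = 5 would create new stopping points and raise the stop probability at a true rate of 20% from 0.301 to 0.415. The objection does not hold against acting early on the existing patient-12 boundary, which changes no decision.

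**Size.** The gain is small if progression is uncommon: about half a patient per trial at 20%, and almost none at 10%. The larger figures depend on assumed high rates, and the averages among stopped trials are conditional. This stands.

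**Individual harm.** A reader might infer that patients who progress are left on a failing regimen until patient 12. They are not: 7.2.5 sends any patient with CT progression to cisplatin RT, whatever the rash. The exposure at issue is that of newly entered patients. Section 17.2 also argues that RT would start in about the usual time, citing a median of 6 weeks from biopsy to treatment in 15 local patients. That tempers any claim about delay, but does not justify entering patients once the stop is certain.

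**Practice.** Each CT result sets that patient's treatment, so the team sees progressions as they occur, and nothing in the plan bars an earlier stop. But nothing requires one either. It is also unclear whether the 12 patients in 16.8 are enrolled, treated or evaluated, and whether accrual pauses for the twelfth CT. If it pauses, the saving falls by about the half patient given above.

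**Conclusion.** The point holds as a gap in the timing of the stopping rule. The boundary itself is computed correctly. With 4 progressions among the first 4 to 11 patients the stop is certain, yet as written between 1 and 8 more patients can enter before the rule is applied. How often this happens depends on a rate that the documents do not give: it is rare at 10%, about one trial in six at 20%, and more likely than not at 40% and above. The calculation assumes independent patients with a common progression rate and a CT result before the next entry. The last assumption slightly overstates the saving.

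Two wording matters in 16.8 do not affect this result. The table labels k as responders although the rule counts progressions, and the note after the table on updating the prior cannot alter the first look.

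**What to change.** Add to 16.8 and to 1.2.1: *If a 4th progression is recorded before 12 patients have been evaluated, the n = 12 boundary is already met and the trial is stopped at that point, as it would be at the n = 12 monitoring.* Keep the rest of the schedule, with a check after every patient from patient 12 on. While editing 16.8, define k as the number of progressions so that the new sentence and the table agree.

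The change uses only the plan's own number and its own stopping action. It needs no extra assessment, because every patient's CT is already read after the third dose. Overall stopping probability and planned sample size are unchanged. The only cost is that a trial stopped this way has fewer patients behind its estimate of the progression rate, and that trial would have stopped at patient 12 in any case.

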17.1 Subject Population

The study population for this protocol is advanced stage III/IV head and neck squamous cell carcinoma of the oropharynx, larynx, and hypopharynx who have not yet received any treatment for their cancer.

17.2 Potential Risks

Radiation therapy for advanced head and neck SCC is always a difficult and potentially hazardous treatment, but in turn often is curative and organ preserving (as opposed to a laryngectomy or large surgical procedure). It routinely entails the risk of fatigue, skin reaction, painful mucositis requiring PEG tube feeding, permanent dry mouth, as well as the risks associated with cisplatin (lowered blood counts, nausea and vomiting, renal damage and ototoxicity) and cetuximab (rash). These toxicities are common to any radiation therapy patient for this disease, and at least for the radiation effects, largely unavoidable.

In this protocol we will select out the partial responders to 3 weeks of neoadjuvant cetuximab, giving these patients cetuximab EBRT and non responders cisplatin EBRT. Therefore, those patients receiving cetuximab instead of cisplatin will be spared the toxicity associated with cisplatin.

The possible added danger of this protocol is that patients who are not responsive to cetuximab may have their definitive treatment with cisplatin EBRT delayed. However, the PI recently selected 15 patients at Rutgers New Jersey Medical School - Newark (where we anticipate most of the patients will come from) and determined the time from biopsy to start of chemoRT or cetuximab RT. The average time was 6.8 wks and median 6 wks. Therefore, we anticipate that the patients on this protocol will start RT in a similar timeframe as they would if they were off protocol. In those patients who would normally have received cetuximab anyway, on this protocol they receive a 3 week loading dose instead of the usual 1 week, so receive an extra 2 weeks of cetuximab prior to RT. Again, we think that in this protocol they would likely start RT in a similar timeframe as they would off protocol.

17.3 Consent Procedures

Current FDA, OHRP, NIH, state and institutional regulations concerning informed consent will be followed. An IRB approved written informed consent document that embodies the elements of informed consent is required §46.116.

1. The investigator shall explain participation is voluntary and all aspects of the study, purpose of the study, treatment plan, procedures, risks, benefits, alternatives, and the right to refuse and withdraw at any time without penalty in lay language.
2. The investigator will answer all the patient's questions regarding the study.

3. The investigator shall give the patient adequate opportunity to read and take home to discuss with family and friends.
4. If the patient decides to participate in the study, he/she will be asked to sign the Informed Consent Document. A copy of the signed Informed Consent Document will be given to the subject and this will be documented in the patient's medical record.
5. The investigator shall inform all patients they have the right to refuse study participation and withdraw their participation at any time without penalty and will be treated without prejudice.

17.4 Non-English Speaking Patients

Where informed consent is documented in accordance with §46.117(b)(1), the written consent document should embody, in language understandable to the subject, all the elements necessary for legally effective informed consent. Subjects who do not speak English should be presented with a consent document written in a language understandable to them.

1. An IRB approved short form written document shall be presented in a language understandable to the subject.
2. The IRB approved English informed consent document may serve as a summary.
3. An interpreter fluent in English and the patient's language shall present the English IRB consent form offered, read it and orally present it to the patient.
4. Through the interpreter, the investigator will explain participation is voluntary and all aspects of the study, the purpose of the study, treatment plan, procedures, risks, benefits, alternatives, and the right to refuse and withdraw at any time without penalty in lay language.
5. Through the interpreter the investigator will answer any questions the patient may have.
6. The investigator shall give the subject adequate opportunity to take the IRB approved English informed consent document home for review by family and/or friends who are fluent in English and the language understandable by the patient.
7. If the patient decides to participate in the study, he/she will be asked to sign the short form document.
8. The IRB approved informed consent document will be signed by the person obtaining consent as authorized under the protocol
9. The written short form document and the English informed consent document will be signed by the witness.
10. When the person obtaining consent is assisted by a translator, the translator may serve as a witness.

11. A copy of the signed IRB approved short form document and the English informed consent document will be given to the subject and this will be documented in the patient's medical record.

12. Through the interpreter, the investigator shall inform all patients they have the right to refuse study participation and withdraw their participation at any time without penalty and will be treated without prejudice.

Regarding the photos of face and upper chest, note that these are not routine, but are done for research purposes in this protocol, as the presence/absence of folliculitis determines the chemotherapy that is received concurrently with radiation

17.5 Potential Benefits

Potential benefits to the patients and to the head and neck population is clear- if we can select out the patients who will be treated well with a high locoregional control rate with cetuximab EBRT, then those patients will be able to escape the higher toxicity associated with cisplatin EBRT, such as increased mucositis, dysphagia and need for PEG, nausea and vomiting, pain and need for narcotic pain medication, hematologic toxicity, renal toxicity and ototoxicity. There is a potential benefit for both HPV + and – patients, as both may potentially receive less toxic therapy- perhaps even more so for the HPV + patients, as they should have a better prognosis, and may benefit from de-escalation of therapy.

17.6 Risk-Benefit Ratio

This study has a very reasonable risk benefit ratio. The standard for these advanced HNSCC patients is either cisplatin EBRT or cetuximab EBRT, and there are no clear criteria to decide which therapy is optimal (10% OS benefit in the Bonner cetuximab RCT vs 6.5% OS benefit for concurrent chemotherapy in MACH NC meta analysis). Older patients with worse performance status often receive cetuximab EBRT due to the gentler toxicity profile. The risk is that cisplatin EBRT is superior to cetuximab EBRT and that some patients will be treated on an inferior regimen. As it is unclear that one regimen is superior to the other, and patients are being treated off protocol on either regimen, it is difficult to assess this risk as real or not.

The benefit is that if we can select out the patients who will be treated well with a high locoregional control rate with cetuximab EBRT, then those patients will be able to escape the higher toxicity associated with cisplatin EBRT.

17.7 Gender and Minorities

This protocol is open to both men and women and all races.

18. Economic/Financial Considerations

The treatment modalities of this protocol (radiation, cisplatin, cetuximab) are standard of care and so will be paid per usual, by insurance or government agencies (charity care, medicare, Medicaid). The molecular correlates include RNA sequencing and testing for DNA mutations using FoundationOne™ (or other certified genomic analysis facility) assay. The Cancer

Institute of New Jersey (via Precision Medicine) will pay for RNA sequencing. We have been in negotiations with FoundationOne™ (or other certified genomic analysis facility) to have them perform the DNA mutation testing gratis, but as of 11/26/13, have nothing in writing—therefore we will collect the paraffin blocks (which will keep for many years) as described in the protocol, and DNA mutation testing will depend on FoundationOne™ (or other certified genomic analysis facility) doing the test for free, or PI/sub-investigators obtaining alternate funding.

19. Publication of Research Findings

The policies and procedures of Rutgers Cancer Institute of New Jersey legal department (see: Investigator's Handbook) will govern publication of the trial. It is expected that the results of this trial will be submitted for publication in a timely manner following the conclusion. The PI, and all co-authors prior to submission or use, must review any abstract or manuscript.

[figure not shown]
